7. TRIAL MATERIALS

7.1. Trial Product (s)

Allogenic amnion chorion membrane (ACM), BioXclude, is a minimally manipulated allograft amnion chorion tissue for use as a wound covering in dental surgery. It has been widely used in dentistry. Its unique physical and biological properties provide the benefits of a growth factor and an occlusive barrier. The tissue used in BioXclude is obtained from consenting mothers who donate their placentas after elective caesarian section delivery. The amnion chorion tissue is processed using a patented tissue processing technology (Purion®,) designed to cleanse and maintain the delicate structures of the tissue. Following processing and dehydration, the allografts are packaged and terminally sterilized. This processing methodology allows for

retention of the biological factors found in native amnion chorion tissue.

Collagen dressing (Collagen Patch®, Zimmer) is used to cover wound in dental surgery. It can adhere to the wound and retain its structural integrity even when wet. It is known to control bleeding and stabilize blood clots as well as protect the wound bed while accelerating the healing process.

7.2. Storage and Drug Accountability

BioXclude membrane and Collagen dressing will be stored at ambient temperature in its original packaging following the manual instruction. The expiration date for the product is recorded on the product container labeling as year (4 digits) and month (2 digits) and the product expires on the last day of the month indicated. Expiration date printed on the labeling is valid as long as product is stored at ambient temperature and in an unopened foil pouch/packaging. Once the product is expired, the material will be discarded.

8. TREATMENT

8.1. Rationale for Selection of Treatments

All subjects need FGG procedure and FGGs are harvested for clinical and research purposes. The treatments are conducted following general clinical principles. The details of procedure are mentioned in section 6.3.

8.2. Specific Restrictions / Requirements

Patients will be prescribed an analgesic (Ibuprofen, 600 mg, q.i.d; if the patient cannot take ibuprofen, 500mg acetaminophen, q.i.d will be prescribed). A disinfectant solution (Chlorhexidine digluconate, 0.2% solution) will be prescribed but the patient will only apply the solution to the recipient site using a monojet syringe (q 8 hours, 10 days). An individualized protective stent will be given to the patient. The patient will be instructed to wear the stent overnight after the surgery and continue wearing it for 10 days. The patient will be instructed to take liquid diet for the first 2 days then soft diet till the 10th day. Sutures at the FGG site will be removed 4 days after surgery.

8.3. Blinding

The surgeons cannot be blinded because the surgeons will be told which dressing should be placed on the specific site. Patients will be blinded given they will not know how the surgical group will be assigned. The patients will be informed of benefits of all the procedures and realize all procedures are supported by scientific evidence.

9. SAFETY MEASUREMENTS

9.1. Definitions

All unanticipated problems will be reported in this study. The Committee For the Protection of Human Subjects (CPHS) considers unanticipated problems to be any

incident, experience, or outcome that meets all of the following criteria:

Is unexpected in terms of nature, severity, or frequency given a) the research procedures that are described in the IRB-approved research protocol and informed consent, and b) the characteristics of the subject population being studied;

Is related or possibly related to participation in the research (possibly related means there is a reasonable possibility that the incident, experience, or outcome may have been caused by the procedures involved in the research); and

Places subjects or others at a greater risk for physical, psychological, economic, or social harm than was previously known or recognized.

An incident, experience, or outcome that meets the 3 criteria above will generally warrant consideration of substantive changes in order to protect the safety, welfare, or rights of subjects or others. Examples of corrective actions or substantive changes that might need to be considered in response to an unanticipated problem include the following:

Changes to the research protocol initiated by the investigator prior to obtaining IRB approval to eliminate apparent immediate hazards to subjects

Modification of inclusion or exclusion criteria to mitigate newly identified

risks Implementation of additional procedures for monitoring subjects

Suspension of enrollment of new subjects

Suspension of research procedures in currently enrolled subjects

For this study, a severe adverse event (SAE) is defined as an unanticipated problem occurring during the study that fulfills 1 or more of the following criteria:

1. Results in death
2. Is immediately life-threatening†
3. Requires inpatient hospitalization or prolongation of existing hospitalization
4. Results in persistent or significant disability or incapacity
5. Is a congenital abnormality or birth defect
6. Is an important medical event that may jeopardize the subject or may require medical intervention to prevent one of the outcomes listed above

Hospitalization for elective procedures or surgeries will not be considered SAEs, nor will inpatient hospitalizations for convenience.

Pregnancy in women with childbearing potential should not be reported as an SAE, but if pregnancy occurs, it must be reported in accordance with the procedures described in Section 6.2. Pregnancy will not be regarded as an SAE unless there is suspicion that a study intervention may have interfered with the effectiveness of a contraceptive medication and the event meets the criteria for an unanticipated problem. If the pregnancy results in an outcome other than a normal birth or elective abortion of a healthy fetus, it will be reported as an SAE.

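### Section 9.1 makes every SAE a subset of unanticipated problems, so a death or non-elective hospitalization judged unrelated to the research is not collected or reported as an SAE

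*Combined protocol and SAP*

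**What the plan says.** Section 9.1 first defines an unanticipated problem as an "incident, experience, or outcome that meets all of the following criteria". There are three criteria:

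- "Is unexpected in terms of nature, severity, or frequency given" the approved research procedures and the population studied;
- "Is related or possibly related to participation in the research";
- "Places subjects or others at a greater risk for physical, psychological, economic, or social harm than was previously known or recognized".

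It then states that, in this trial, "a severe adverse event (SAE) is defined as an unanticipated problem occurring during the study that fulfills 1 or more of the following criteria". The six criteria that follow are the usual seriousness criteria, among them death, immediate threat to life and inpatient hospitalization. A separate sentence provides that "Hospitalization for elective procedures or surgeries will not be considered SAEs", and treats admissions for convenience in the same way.

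The pregnancy paragraph that closes 9.1 says a pregnancy is an SAE only if interference with contraception is suspected "and the event meets the criteria for an unanticipated problem". If, however, the pregnancy has "an outcome other than a normal birth or elective abortion of a healthy fetus, it will be reported as an SAE", and here no such condition is attached.

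Section 9.2 collects serious adverse events by express reference to 9.1, has staff ask about SAEs at each visit, and requires an SAE to be reported to CPHS within 24 hours of the investigator becoming aware of it. Section 11.2b plans a table of SAEs and gives no definition of its own. It also plans a by-subject listing of the adverse events noted, including relationship to procedure. Section 6.3e, on discontinuation, gives life-threatening disease and hospitalization as examples of a serious adverse event and does not mention the three tests.

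**The concern.** Seriousness, expectedness and relatedness are separate properties of an event. Section 9.1 combines them, so the investigator's judgement on expectedness, relatedness and added risk decides whether a death or hospitalization counts as an SAE at all. Those judgements ought to be recorded about a serious event, where they can be reviewed. If they act as an entry condition, an event screened out at the start is missing from the SAE record when a later case suggests a link.

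Under 9.1 as written, a subject admitted for an acute illness judged unrelated to the surgery or dressing has no SAE. Such events are possible in this population, because Section 3.3 admits subjects with controlled systemic conditions such as hypertension. What is at stake is the completeness of the safety record.

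**Working it through.** **Logic of the definition.** No figure in the plan is at issue, so the check is to write out the rule and follow it through the document. Section 9.1 gives:

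SAE = (unexpected AND related or possibly related AND greater risk than known) AND (at least one of six seriousness criteria).

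For a death or non-elective hospitalization the last bracket is true. The three remaining yes/no tests give 2 × 2 × 2 = 8 combinations. One of them (yes, yes, yes) is an SAE and the other 7 are not, so failing a single test is enough to exclude the event. This counts logical cases and does not say how likely each one is.

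**Where the definition is used.**

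| Section | Use of the term | Effect on a serious event that fails a test |
|---|---|---|
| 9.2, collection | Cites 9.1 | Not collected as an SAE |
| 9.2, enquiry at visits and 24-hour CPHS report | Same term, same section | Outside both |
| 11.2b, SAE table | No definition given | Outside the table, by inference |
| 11.2b, adverse event listing | Adverse events noted | May appear, if noted |
| 9.2, monthly report to PIs | Severe pain, bleeding, swelling; oral health events | Included only if of these kinds |
| 6.3e, follow-up after discontinuation | Examples only, no three tests | Followed up, on a plain reading |
| 9.1, abnormal pregnancy outcome | No unanticipated-problem test | Reported as an SAE |

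The last two rows show that the term is not used uniformly. Section 9.1 also expands the abbreviation as *severe*, while 9.2 and 11.2b expand it as *serious*. The separate exclusion of elective and convenience admissions would be largely redundant if every SAE already had to be unexpected, related and a new risk.

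**Size.** Inputs: 19 subjects (Section 3.1) and follow-up to 8 weeks after surgery (Section 4). The documents give no SAE rate. The range of 0.02 to 0.10 serious events per subject-year is an assumption.

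- Exposure if all complete: 19 × 8 = 152 subject-weeks; 152 / 52 = 2.92 subject-years.
- Expected serious events: 2.92 × 0.02 = 0.06, to 2.92 × 0.10 = 0.29.
- Effect of one omitted subject on the proportion with an SAE: 1/19 = 5.3 percentage points, or 1/15 = 6.7 points with the 15 subjects the plan expects after dropout.

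The exposure is approximate. SAE collection starts at enrollment, which lengthens it slightly, and dropout shortens it.

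**The case against.** The strongest reply is that the nesting may be deliberate. The three-part test is presented as CPHS's own, and CPHS receives the 24-hour report, so limiting an urgent report to events meeting its test is coherent. This stands as far as the trigger goes: the documents cannot settle what CPHS requires, and the fix leaves that open. It does not explain why the same test should govern which events are collected and tabulated as SAEs.

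A second reply is that the three routes of exclusion are not equally likely. The stated risks (Section 2.4) are infection, pain, swelling and bleeding. A death would almost always be unexpected, and if it were possibly related it would ordinarily imply a new risk. This is fair, and it is why unrelated events are the main gap.

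Third, there are backstops. Staff who ask about SAEs would in practice hear of a hospitalization, the 11.2b listing could show it, and the monthly report covers many expected complications of the procedure. These soften the problem. However, the monthly report does not reach an unrelated systemic event, the case report forms are directed at oral health, and neither the listing nor the monthly report triggers the 24-hour report.

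Finally, the numbers are small, the assumed rates have no basis in the documents, and the percentage-point figures are simply 1/n. Each subject receives both dressings, so one missed systemic event would not distort the comparison between them. All of this is accepted. It bears on how much the defect matters and leaves the definition itself unchanged.

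**Conclusion.** The concern holds: the definition is wrong as written. On the plain text of 9.1 and 9.2, a death or non-elective hospitalization that is judged unrelated, expected or no new risk is neither collected as an SAE nor reportable within 24 hours. Its absence from the SAE table is an inference, because 11.2b does not cite 9.1. Sections 6.3e and the pregnancy paragraph of 9.1 use the term more broadly, so staff working from different sections could classify the same event differently.

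The practical size is modest. Under the assumed rates, well under one serious event of any kind is expected, and only some of those would be lost. There is no effect on the efficacy analysis. The change should be made because the defect is clear, it concerns the most serious events a trial can record, and correcting it is cheap.

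**What to change.** - Define a serious adverse event as any untoward medical event that meets one of the six criteria already in 9.1, whatever its expectedness or relatedness. Keep the existing exclusion of elective and convenience hospitalizations.
- Use that definition for collection, enquiry at visits, follow-up and the SAE table.
- Record expectedness for each event beside the relationship to procedure that 11.2b already lists.
- Keep unanticipated problems as a separate category, and state which category triggers the 24-hour report after confirming this with CPHS.
- Reconcile 6.3e, 9.1 (including the pregnancy paragraph), 9.2 and 11.2b, and use *serious* throughout.

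The cost is a wording amendment with IRB review. Given the exposure, any added recording or reporting should be slight.

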9.2. Collecting, Recording and Reporting of Adverse Events

Examination and close follow-up of parameters capturing subjects' oral health will be collected on case report forms (CRFs). These will be completed at every study visit, and data will be compiled into a pre-specified format and reviewed monthly by the PI for safety oversight.

Serious adverse events (as defined in Section 9.1) will be collected from the time of enrollment until the last clinic visit and will be recorded in the electronic health records (EHR) system. At each study visit, the clinician or investigator will inquire about the occurrence of SAEs since the last assessment. The investigator will review all source documentation related to study procedures for evidence of SAEs. Events will be followed for outcome information until they return to baseline or stabilize, or

until 30 days after study completion or subject discontinuation. Subjects who have an SAE that is ongoing 30 days after study completion or discontinuation will be referred to an appropriate practitioner for continued care.

Upon learning that a subject has experienced an SAE, the investigator must report the event to CPHS within 24 hours after becoming aware of the event.

On a monthly basis, the following events will be reported to every PI:

Number of subjects experience severe complications and number of subjects enrolled. Severe complications include severe pain (VAS>6), continuous bleeding and severe swelling that needs prescription to control.

Duration of observation of subjects experiencing severe complications and duration of observation of subjects enrolled.

Any tooth loss, abscess, or other adverse oral health development requiring therapy or other intervention and the etiology (as captured in the dental history)

Every PI will review the monthly reports for any safety signals.

9.3. Safety Monitoring Plan

The purposes of the clinical monitoring activities are to ensure that the rights of human subjects are protected, the study is implemented in accordance with the protocol, and the integrity of study data is maintained.

All subjects will be monitored for postoperative healing and tissue response at a regular interval while the entire oral health will be maintained throughout the study period.

10. DATA ANALYSIS

10.1. Data Quality Assurance

Data and measurements will be checked by two separate investigators ([name], [name]) as well as analyzed statistically to ensure that the data obtained is accurate, complete and reliable.

10.2. Data Entry and Storage

Case report forms (CRFs) will be completed and stored in a locked file cabinet in the PI's office located at UTSD. Data will be entered electronically in excel spreadsheets, and images will be stored electronically; both will be stored on the PIs work computer in a locked office and password protected.

11. SAMPLE SIZE AND STATISTICAL METHODS

11.1. Determination of Sample Size

The pilot project will use a convenient sample size based on the budget. We will recruit 19 patients in total, and with a dropout rate of 15%, we will have a sample size of 15.

With 15 patients, we can detect an effect size as small as 0.7 between two treatments for the two main outcomes (the area of healing and VAS pain score at

week 2), by a paired t test assuming a within-subject correlation of 0.6 at the significance level of 0.05 with 80% power. Considering this is a pilot study, Bonferroni correction is not necessary.

11.2. Statistical and Analytical Plans

a. General Considerations

We will present means and standard deviations for completeness of the report. The statistical significance level to test the primary endpoint was set at $p<0.05$, a priori.

b. Safety Analyses

Safety will be evaluated by tabulations of adverse events and will be presented with descriptive statistics at baseline and follow-up visits each month.

Adverse events will be classified as severe complications and summarized for baseline and follow-up visits.

All information pertaining to adverse events noted during the study will be listed by subject, detailing verbatim given by the investigator, preferred term, date of onset, date of resolution, severity, and relationship to procedure. The onset of adverse events will also be shown relative (in number of days) to the day of performing the surgery.

A tabulation of Serious Adverse Events (SAEs) will be provided by subject within treatment groups. The proportion of subjects in each treatment group reporting adverse events that occur in ~ 3% in either treatment group will be compared using Bayesian methods. The specific preferred terms analysed will be those that are reported by at least five percent of the subjects in either treatment group.

c. Statistical Analysis Plan:

We will explore the difference between the two treatments for outcomes including the degree of epithelialization, the size of wound area, color match, bleeding condition, pain, sensibility, and outcomes from Gingival specimens by paired t test or McNemar's test depending on the variables.

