1.2. Rationale and justification for the Study

a. Rationale for the Study Purpose

So far, there is no strong evidence supporting the clinical impact of any dressings or membranes on the healing of the FGG donor site. It is very important to assess the effects of the allogenic amnion chorion membrane on the wound of the FGG donor site given this membrane has the potential to improve wound healing and reduce complications.

b. Rationale for Materials Selected

The ACM (allogenic amnion chorion membrane, BioXclude®, SNOASIS MEDICAL) is a commercial product and has multiple sizes available. It has been used for tissue healing and tissue regeneration in dentistry. Based on the available evidence, it has the potential to improve wound healing of the FGG donor site. The collagen dressing, CLD (Collagen Patch®, Zimmer), is a common product used for tissue healing in dentistry (Shanmugam et al. 2010). It is selected as a dressing material to cover the wound in the control group.

c. Rationale for Study Population

The study will recruit subjects who need free gingival graft surgery. The dressings, ACM or CLD, will be placed in the wound of the FGG donor site. These subjects

should be systemically healthy and are able to receive FGG surgery.

d. Rationale for Study Design

It is a randomized controlled and split-mouth design study. The randomized controlled trial (RCT) is usually considered the gold standard for a clinical trial and it is able to provide the highest level of evidence within all the study designs (Howick et al. 2011). The split-mouth design is a popular design in oral health research. Two treatments (test and control) are randomly assigned to either the right or left halves of the dentition/palate. This design removes a lot of inter-individual variability from the estimates of the treatment effect given two treatments are performed in the same subject (Lesaffre et al. 2009).

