6. METHODS AND ASSESSMENTS

6.1. Randomization and Blinding

Site allocation (right or left side of the palate) to the two groups (ACM or CLD) will be performed by the investigators before the surgeon harvests FGGs, based on computer-generated randomization (R Statistical Software). Patients will be blinded because they will not know which dressing is in the test group or the control group.

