6.3. Study Visits and Procedures

a. Screening Visits and Procedures

Study protocol and consent forms will be approved by the Institutional Review Board at the University of Texas Health Science Center at Houston. The trial will be registered with ClinicalTrials.gov. The clinicians in UTSD will be told the information of this clinical trial. The potential subjects will be identified in the clinic of Department of Periodontics, for initial screening. The principal investigator will confirm the eligibility of these patients.

All patients will sign the consent forms and are informed of the details of study procedures as well as potential complications. After informed consent is obtained, the surgery will be scheduled as the first visit. An impression will be taken to make the stent before the surgery.

b. Study Visits and Procedures

Patients will have FGGs harvested from two sites on the palate (right and left; the area between canine to first molar). In addition to the FGG wounds, two palatal gingiva biopsies will be harvested. The size of the FGG will be standardized (8mm (width) x 10mm (length) x \approx 1.5mm thickness). FGGs will be harvested by the #15 blade with the assistance of a template stent. Two FGGs will be used based on the patient's need. If the patients need grafts larger than two standardized FGGs in one procedure, the patients will be excluded from the study. The biopsies of palatal gingiva will be harvested by a tissue punch and the size is standardized (4mm (diameter) x \approx 1.5mm thickness). The area of biopsy will be at least 3mm away from the FGG wound. Biopsies and FGGs will be harvested in the area between maxillary canine and first molar where tissue grafts are commonly harvested from (Reiser et al. 1996). These wounds can be completely healed even without placing any dressing materials (Harris et al. 2007). Dressing materials are used to improve healing and reduce complications. The wounds of FGG and biopsy will be covered with an allogenic amnion chorion membrane (ACM, BioXclude®) or a collagen dressing (CLD, Collagen Patch®) based on the randomization table.

Clinical Measurements

The donor sites of FGG will be evaluated on 4 days, 10 days, 2 weeks, 3 weeks, 4 weeks, 6 weeks, 8 weeks after the surgery (7 follow-up visits in total). Healing of the donor site will be analyzed based on (1) the degree of epithelialization, (2) the size of wound area, (3) color match and (4) bleeding condition.

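### Section 11.2b words the safety analysis for parallel groups although every patient receives both dressings: events need a site-attribution rule, and donor-site comparisons need to be stated as within-patient (minor)

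*Combined protocol and SAP*

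**What the plan says.** Section 1.2d justifies the split-mouth design by its lower variability "given two treatments are performed in the same subject". Section 6.1 defines the groups by side of the palate: "Site allocation (right or left side of the palate) to the two groups (ACM or CLD". Section 6.3b confirms that both sides are used in everyone: "Patients will have FGGs harvested from two sites on the palate (right and left; the area between canine to first molar".

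The safety analysis in section 11.2b gives two rules for groups. For serious events: "A tabulation of Serious Adverse Events (SAEs) will be provided by subject within treatment groups". For adverse events generally: "The proportion of subjects in each treatment group reporting adverse events that occur in ~ 3% in either treatment group will be compared", by Bayesian methods. No model, prior or pairing is given. The by-subject listing in the same section covers term, dates, severity and relationship to the procedure; it mentions neither side nor dressing.

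Section 11.2c handles the outcomes differently. It plans within-patient tests for a list that includes "color match, bleeding condition, pain, sensibility, and outcomes from Gingival specimens by paired t test", or McNemar's test, depending on the variable.

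On serious events, section 9.1 says that "a severe adverse event (SAE) is defined as an unanticipated problem occurring during the study that fulfills 1 or more of the following criteria". The criteria then listed include death, hospitalization and disability.

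**The concern.** Subjects in each treatment group is a parallel-group phrase. Here the ACM subjects and the CLD subjects are the same people, so a table of subjects by group does not separate the dressings unless each event is first tied to a side. Two gaps follow.

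First, some events have no donor-site origin. A reaction to a medicine, or a problem at the recipient site (listed among the study risks in section 2.4b), belongs to neither dressing. The stated table would show it under both or put it somewhere by a choice nobody has written down.

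Second, some donor-site events can be tied to a side but are not named in section 11.2c. Sections 2.4b and 9.2 mention swelling, infection and abscess. For these the plan does not say that the comparison is within patient.

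What is at stake is the complications part of the alternative hypothesis in section 2.1, which expects fewer of them with ACM. If the side is not noted when an event occurs, it may not be recoverable later.

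**Working it through.** **1. The plan's own figure.** Section 11.2b states no sample size or power. The nearest figure is in section 11.1: 15 patients, effect size 0.7, within-subject correlation 0.6, significance level 0.05, power 80%. Taking the test as two-sided (not stated), the standardized paired difference is 0.7/√(2 × (1 − 0.6)) = 0.783. With 14 degrees of freedom the power is 80.5%. The figure reproduces, and it does so by using the pairing. The efficacy plan therefore treats the patient as the pair; section 11.2b does not say so.

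**2. An event with no donor site, counted under both dressings.** Each group's rate rises by 1/N: 1/19 = 5.3 points, 1/15 = 6.7 points. The difference changes by 1/N − 1/N = 0. Each dressing's rate is inflated but the contrast is not. If the event is instead placed under one dressing, the contrast shifts by the same 5.3 to 6.7 points.

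**3. Does pairing matter for donor-site events?** The documents give no event rates, so the counts below are assumptions for 15 patients.

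- Independent SE of the difference = √(p₁(1 − p₁)/n + p₂(1 − p₂)/n).
- Paired SE = √(b + c − (b − c)²/n)/n, where b and c are the numbers of patients with the event on one side only.
- Posterior probability that CLD has the higher rate: independent uniform priors for the two groups, against a four-cell Dirichlet prior with 0.5 per cell, which has the same uniform margins.

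| Assumed counts (both sides / CLD only / ACM only) | Independent SE | Paired SE | Posterior, independent | Posterior, paired |
|---|---|---|---|---|
| 3 / 6 / 0 (9 of 15 against 3 of 15) | 0.163 | 0.127 | 0.985 | 0.997 |
| 0 / 6 / 0 (6 of 15 against 0 of 15) | 0.126 | 0.126 | 0.997 | 0.997 |

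For the first row, independent: √(0.24/15 + 0.16/15) = 0.163; paired: √(6 − 36/15)/15 = 0.1265. When some patients have the event on both sides, ignoring the pairing changes the answer. When none do, it makes almost no difference to these quantities.

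**4. What a paired test can show at this size.** With all discordant patients in one direction, the exact two-sided McNemar p value is 2 × 0.5^k: k = 5 gives 0.0625 and k = 6 gives 0.031. Six patients are 6/19 = 32% or 6/15 = 40% of the sample. This is a threshold, not a forecast of how many events there will be, but it is a reason to report an interval beside any test.

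**The case against.** The best defence is that section 6.1 defines the groups by site. Then the proportion of subjects in each group means the share with an event on the ACM side against the share with one on the CLD side, and those are the two margins that a McNemar comparison uses. No independent-groups test is planned, Bayesian methods do not exclude a paired model, and the outcome list in section 11.2c is open-ended. This largely stands for donor-site events: the text can be read coherently. It still does not state pairing, and it gives no place to events without a donor site.

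Three stronger readings are tempting and not supported.

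- *No SAE can be assigned to a dressing.* The criteria in section 9.1 describe how serious an event is, not where it arose, and an SAE there must also be unexpected and at least possibly caused by the research. A hospital admission for bleeding from one palatal wound would qualify and would belong to one dressing. Only SAEs without a donor-site origin lack a group.
- *The form does not record the side.* The case report form (Appendix 1) was not available, so absence of the field is not shown.
- *The percentage filters distort the comparison.* Besides the threshold of about 3%, the plan says "The specific preferred terms analysed will be those that are reported by at least five percent of the subjects in either treatment group". Read as minimums, neither drops anything at the planned size, since one patient is already 5.3% of 19 or 6.7% of 15, and all events are listed by subject in any case.

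**Conclusion.** The point holds and is minor. The wording of section 11.2b does not fit the design. Taken literally it puts the same people in both groups and leaves events without a donor-site origin to be double-counted or placed arbitrarily. For donor-site events that section 11.2c does not name, the comparison is not stated as within-patient.

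The effect on results is unknown. The documents give no event rates; the illustration rests on assumed counts and shows that pairing may matter or may not. A reader might infer that the trial's safety conclusions would be wrong or biased toward one dressing. Nothing in the documents shows that: an event counted under both dressings leaves the difference unchanged, bleeding, pain and sensibility already have paired tests, and the main efficacy outcomes are untouched.

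**What to change.** In section 11.2b:

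- Classify each adverse event, including each SAE, as ACM site, CLD site, both sites, or not attributable to a donor site. Confirm that the case report form records this at the time of the event.
- Tabulate site-attributable events and SAEs by dressing. Compare those not already tested in section 11.2c within patient, by exact McNemar's test or a stated paired Bayesian model (with its prior), and give an interval for the paired difference.
- List events and SAEs not attributable to a donor site once per subject, with no dressing group.

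The cost is SAP wording, one form field if it is absent, and IRB review of the amendment under section 12.2. No patients or visits are added.
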